17.2 DECISION RELATING TO THE "STANDARD OF CARE" (I.E. CONTROL)

Factors that will be considered prior to proposing a change in standard of care (i.e.the control) in this platform are summarised in Figure 3. The TMG will propose any change to the "standard" which will require ratification by the TSC. Members with relevant conflicts of interest can comment but will leave the meeting prior to a decision being made.

Figure 3 Factors to consider prior to recommending change in standard of care

18 OVERSIGHT AND MONITORING

18.1 TRIAL MANAGEMENT GROUP (TMG)

Members of the TMG are listed in Table 3. Changes in individuals filling these roles will not require

a protocol update but will be documented in the TMG minutes.

TABLE 3 TRIAL MAN	IAGEMENT GROUP ME	MBERSHIP IN BEACON TRIAL
-------------------	-------------------	--------------------------

Title	Role
Chief Investigator	Chair
Programme Lead	Member
BEACON Senior Statistician	Member
BEACON Junior Statistician	Member
KCTU Senior Trial Manager	Member
KCTU Trial Manager	Member
KCTU Trial Manager	Member
KCTU Pharmacist	Member
KCTU Director of Operations	Member
KCTU Data Centre Lead	Member
Nested Process Evaluation Lead	Member
Health Economist – Within Trial Evaluation	Member
Health Economist – Economic Modelling	Member
PPI Member	Member
PPI Member	Member
mySkinomics (affiliated mechanistic research) Chief Investigator	Member
National Eczema Society Chief Executive	Member
KHP-CTO Clinical Research Associate for BEACON	Observer

18.2 PATIENT LIASION ADVISORY GROUP (PLAG)

There are three patients in the BEACON trial development team (co-applicants), all with lived experience of moderate to severe eczema, systemic therapy and/or trial therapy. They are reflective of the planned trial population and have provided in-depth viewpoints to the team by drawing on their personal experience. In addition to our patients, [name], Chief Executive of the National Eczema Society, is also a member of the trial development team (co-applicant), bringing a third-party perspective of a much wider group of patients.

To reduce burden the PLAG will only be invited to relevant TMG meetings or consulted separately throughout the lifetime of the trial thereby contributing to all the key decisions including but not limited to input into patient facing materials such as information leaflets, newsletters and the website to ensure information is understandable, comprehensive and focussed on the aspects that matter to participants.

18.3 TRIAL STEERING COMMITTEE (TSC)

The TSC will be composed of five independent members. The TSC is an executive committee, reporting to the funder (NIHR) and the sponsor. The TSC is formally appointed by NIHR and members will receive individual letters from NIHR confirming their role. Independent members will be independent of the Sponsor organisation and of any recruiting study sites.

The trial may be prematurely discontinued by the Sponsor, Chief Investigator or Regulatory Authority on the basis of new safety information or for other reasons given by the Data Monitoring Committee, Trial Steering Committee, regulatory authority or ethics committee.

If the trial is prematurely discontinued, active participants will be informed, and no further participant data will be collected. The Competent Authority and Research Ethics Committee will be informed within 15 days of the early termination of the trial.

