7.3 DISCONTINUING ALLOCATED INTERVENTIONS

Participants may temporarily or permanently stop taking study drug at their discretion or that of the site investigator. In all cases every effort should be made to ensure follow up data is collected per protocol to the end of the trial, unless the participant is formally withdrawing from further data collection (see section 5.5). The clinical study report will include reasons for participants discontinuing study medication.

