10 ADVERSE EVENT MANAGEMENT AND REPORTING

All adverse events will be recorded from consent to the end of study visits in the participants medical notes, the AE source data worksheets and the eCRF. SAE's will be additionally reported, within 24 hours of site becoming aware of the event, to the KHP-CTO.

All SAEs, SARs and SUSARs will be reported immediately (and certainly no later than 24hrs) by the Investigator to the KHP-CTO for review in accordance with the current Pharmacovigilance Policy and as per the instructions on the SAE report form.

The Medicines for Human Use (Clinical Trials) Regulations 2004 and Amended Regulations 2006 gives the following definitions:

- Adverse Event (AE): Any untoward medical occurrence in a participant to whom a medicinal product has been administered, including occurrences which are not necessarily caused by or related to that product.
- Adverse Reaction (AR): Any untoward and unintended response in a participant to an investigational medicinal product which is related to any dose administered to that participant.
- Unexpected Adverse Reaction (UAR): An adverse reaction the nature and severity of which is not consistent with the information about the medicinal product in question set out in the summary of product characteristics (SmPC) for that product.
- Serious adverse Event (SAE), Serious Adverse Reaction (SAR) or Suspected Unexpected Serious Adverse Reaction (SUSAR): Any adverse event, adverse reaction or unexpected adverse reaction, respectively, that:
 - results in death
 - is life-threatening
 - required hospitalisation or prolongation of existing hospitalisation (excluding elective or planned procedures)
 - results in persistent or significant disability or incapacity
 - consists of a congenital anomaly or birth defect
- Important Medical Events (IME) & Pregnancy: Events that may not be immediately lifethreatening or result in death or hospitalisation but may jeopardise the participant or may require intervention to prevent one of the other outcomes listed in the definition above should also be considered serious. Although not a serious adverse event, any unplanned pregnancy will also

be reported via the SAE reporting system.

• Adverse Event of Special Interest (AESI): Pre-specified adverse events of interest for which more detailed information will be collected

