10.1.4 FOLLOW-UP OF AES AND SAES

After the initial AE/SAE report, the Investigator is required to proactively follow each participant and provide further information to the Sponsor on the participant's condition. All AEs and SAEs documented at a previous visit/contact and are designated as ongoing, will be reviewed at subsequent visits/contacts. All AEs and SAEs will be followed until resolution, until the condition stabilises, until the event is otherwise explained, or until the participant is lost to follow-up. Once resolved, the adverse event log will be updated. The Investigator will ensure that follow-up includes any supplemental investigations as may be indicated to elucidate the nature and/or causality of the AE or SAE. This may include additional laboratory tests or investigations, histopathological examinations, or consultation with other health care professionals. New or updated information will be recorded on anSAE follow up form, signed and dated by the Investigator. The follow up SAE form should be sent to the Sponsor.

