10.1.5 POST-STUDY AES AND SAES

A post-study AE/SAE is defined as any event that occurs outside the AE/SAE detection period. Investigators are not obligated to actively seek AEs or SAEs in former study participants. However, if the Investigator learns of any SAE, including death, at any time after a participants has been discharged from the study, and he/she considers the event reasonably related to the investigational product, the Investigator will promptly notify the Sponsor.

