12.6 INTERIM ANALYSES (STATISTICAL)

Following discussion with the oversight groups, sponsor and funder as the study progresses, we may include one interim analysis for futility and efficacy. This will control the type 1 error rate for each pairwise comparison and have minimal impact on the power for the final analyses.

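### Section 18.3 ends all data collection if the trial is stopped early, which conflicts with the duty in section 10.1.4 to follow open adverse events and leaves pending outcomes unaddressed

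*Protocol*

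**What the plan says.** Section 18.3 lets the Sponsor, Chief Investigator or regulator discontinue the trial early "on the basis of new safety information or for other reasons given by the Data Monitoring Committee", the Trial Steering Committee, the regulator or the ethics committee. It then fixes the consequence: "active participants will be informed, and no further participant data will be collected". No reason for stopping, type of data or group of participants is excepted.

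Section 10.1.4 sets the rule for events already recorded: "All AEs and SAEs will be followed until resolution, until the condition stabilises, until the event is otherwise explained", with loss to follow-up as the remaining end point. It also requires the investigator to follow each participant proactively and to send updated SAE forms to the Sponsor.

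Other sections bear on the same question:
- Section 10 (opening paragraph): "All adverse events will be recorded from consent to the end of study visits".
- Section 10.1.5: "Investigators are not obligated to actively seek AEs or SAEs in former study participants", but a related SAE that the investigator learns of after a participant has left the study must still be notified promptly.
- Section 7.3, on participants who stop study drug: "every effort should be made to ensure follow up data is collected per protocol to the end of the trial", unless the participant withdraws from data collection.
- Section 12.3 makes a similar commitment for research assessments in all participants and all arms, under the intention-to-treat principle.

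**The concern.** The two rules give a site opposite instructions about the same information. If the trial is stopped because of a safety signal, an investigator with an unresolved SAE on file is told by 10.1.4 to keep following it and by 18.3 to collect nothing more. A safety stop is when the course of open events is most needed, both for the participants and for interpreting the signal that led to the stop.

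There is a second, weaker tension. Participants randomised and treated but not yet at month 6 or month 12 would have no later outcome recorded if the whole trial stopped, whatever the reason. The protocol elsewhere treats complete follow-up as a priority even after treatment ends. Follow-up that is not done at the time may not be recoverable later.

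**Working it through.** No calculation decides this point; it rests on reading the sections together.

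1. **Scope of 18.3.** The trigger is premature discontinuation of the trial. The preceding paragraph of 18.3 lists safety findings and other committee reasons as grounds. The consequence covers participant data without qualification, so on its face it includes safety data.

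2. **Scope of 10.1.4.** It covers all AEs and SAEs and has four end points: resolution, stabilisation, other explanation, loss to follow-up. A terminated trial meets none of them. For an event open on the day of termination, 10.1.4 requires further information and 18.3 forbids collecting it. This is a direct conflict.

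3. **Does the recording period in section 10 resolve it?** It bounds when events are recorded, from consent to the last study visit. It does not say that follow-up of an event already recorded ends there.

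4. **Does 10.1.5 resolve it?** It concerns events arising after the detection period. It lifts the duty to look for events in former participants and keeps the duty to notify related SAEs that come to light. It does not close events that are already known and open. It also shows that the protocol expects some safety data after participation ends, which an unqualified 18.3 does not allow for.

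5. **Outcome data.** Section 7.3 asks for follow-up to the end of the trial after study drug is stopped, and 12.3 asks for it in all participants and arms. Section 20.3 defines the end of the trial as final database lock, and early termination could bring that date forward. Sections 7.3 and 12.3 are therefore in tension with 18.3 rather than in strict contradiction. What is missing is a statement of whether remaining visits of randomised participants go ahead.

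6. **Data already held.** Section 18.3 ends future collection. Nothing in the protocol deletes or excludes data collected before the stop. The nearest rule, on withdrawal of consent in section 5.5, keeps such data and includes them in analysis.

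7. **Size.** The count of outcomes forgone depends on how many participants are short of month 6 or month 12 on the day of the stop. That needs an accrual rate and a stopping date, and the protocol gives neither.

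**The case against.** The best defence is that 18.3 means scheduled research data only and that section 10 safety duties continue regardless. SUSAR reporting under 10.3 is not tied to the trial continuing, and related SAEs that come to an investigator's notice are still notified under 10.1.5. It would therefore be wrong to say that all safety outcomes would be unknown after a stop. What stands is narrower: the limiting reading of 18.3 is not written, and neither 10.1.5 nor 10.3 provides for active follow-up of known open events.

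It is also fair to say that continuing efficacy visits after a whole-trial termination is partly a design preference, and that a regulator or sponsor decision may rule it out. That is why the plan need only state its position on those visits.

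Three stronger readings are tempting, and the documents do not support them.

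- **That outcomes are discarded.** Only future collection stops; existing data remain.
- **That an interim futility or efficacy result would trigger the rule.** Section 12.6 says only that "we may include one interim analysis for futility and efficacy", and frames error control per pairwise comparison. Sections 9.7.1 and 20.2 describe interventions and comparisons closing separately. Nothing says that one comparison's result discontinues the trial. A whole-trial stop after an interim is possible under the open-ended grounds in 18.3, but it is not what 12.6 sets out.
- **That the loss can be put at a definite share.** If one assumed even recruitment of all 536 over 24 to 48 months and a stop at full enrolment, the participants short of month 6 would be 536 × 6/24 = 134 (25%) to 536 × 6/48 = 67 (12.5%). Those short of month 12 would be 536 × 12/24 = 268 (50%) to 536 × 12/48 = 134 (25%). The recruitment period is invented. Even accrual does not fit a trial that began with three arms, added abrocitinib later and extends control recruitment (sections 1.3 and 12.1). The 20% loss to follow-up planned in 12.1 is not deducted either. These figures should not be quoted as the size of the problem.

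**Conclusion.** The conflict between 18.3 and 10.1.4 is real as written. Followed literally, 18.3 would end active follow-up of known open AEs and SAEs at the moment of a safety stop, and no other section exempts them. If the whole trial stopped, outcomes not yet reached would also go uncollected, which sits badly with 7.3 and 12.3. The effect arises only on early termination, leaves data already held untouched, and cannot be expressed as a number of participants from this document. The conclusion rests on the text alone and needs no assumption about accrual, interim analyses or treatment effect. It concerns data collection; clinical care after termination is for the sponsor to settle.

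**What to change.** Reconcile sections 18.3, 10.1.4, 10.1.5, 7.3 and 12.3 by replacing the blanket sentence in 18.3 with one that does two things:

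1. Exempts the section 10 safety data from the stop on data collection, namely follow-up of open AEs and SAEs and reporting of pregnancies through the SAE system. Section 10 provides for reporting an unplanned pregnancy but sets out no pregnancy follow-up procedure, so the exemption should be worded as reporting.
2. States whether the remaining scheduled outcome assessments of participants already randomised continue, subject to the reason for stopping, the participant's consent, and regulator or ethics committee decisions. The wording should refer to assessments still to come. A rule limited to visits already due at the stop would not recover later month-6 or month-12 outcomes.

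The cost is about one sentence in the protocol, plus limited follow-up work that arises only if the trial stops early.

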18.4 DATA MONITORING COMMITTEE (DMC)

The DMC will be composed of three independent members: a statistician and two clinicians. The DMC is an advisory committee, reporting to the TSC. The DMC is formally appointed by NIHR and members will receive individual letters from NIHR confirming their role. Members will be independent of the Sponsor organisations and of any recruiting study sites. The DMC will work to the DAMOCLES guidance⁴⁸.

18.5 **MONITORING**

Monitoring of this trial to ensure compliance with Good Clinical Practice and scientific integrity will be managed and oversight retained by the KHP-CTO Quality Team at KCL.

The Investigator(s) will permit trial-related monitoring, audits, REC review, and regulatory inspections by providing the Sponsor(s), Regulators and REC direct access to source data and other documents (e.g., participants' case sheets, blood test reports etc.).

The KHP-CTO will prepare a site monitoring plan in accordance with local regulatory and REC requirements. At the site initiation visit, the Trial Manager will provide the recruiting site with a BEACON-specific investigator site file and a site pharmacy file to be maintained for the duration of the study.

19 INVOLVEMENT OF PATIENTS AND THE PUBLIC

Patients have been involved from initial conception of this research proposal. The Eczema Priority Setting Partnership of patients and clinicians prioritised the research question: "*What is the best and safest way of using drugs that suppress the immune system when treating eczema?*" Patients have subsequently been involved in all relevant aspects of BEACON to ensure that the study design is acceptable. The PLAG have contributed to the original funding application, pre-trial surveys and the BEACON trial design.

Direct input from these individuals has been supplemented with two online patient surveys promoted through the National Eczema Society, to address specific areas of concern that required a wider range of viewpoints. We had 97 and 51 respondents to these surveys, of which 95% had eczema that was moderate or severe and therefore closely reflected our anticipated trial participants. Through a dedicated workshop session on 12th October 2020, we have also benefitted from the UK Dermatology Clinical Trials Network patient panel input into the trial design. The trial was discussed three times at the UK Dermatology Clinical Trial Network meetings and at UK Translational Research Network in Dermatology meeting, both of which include patient representatives as well as clinicians and researchers.

Having patients involved has meant that the trial has been designed in a way that is acceptable to patients. For example, we were strongly encouraged to minimise any additional patient burden through extra visits, so the follow-up schedule reflects normal practice and our patient survey showed the proposed schedule did not deter many from considering participating. We were unsure of how long patients were likely to be prepared to continue on a medication that was not providing the hoped for levels of effectiveness and it was clear that 3-6 months was acceptable which enabled us to design the trial with a dose adjustment point at 3 months and a switch point at 6 months.

We will continue to work with our existing patient partners throughout the trial i.e. our three patient co-applicants, the UK Dermatology Clinical Trials Network patient panel and wider input via the National Eczema Society.

20 MISCELLANEOUS

20.1 PLANS FOR INDEPENDENT AUDIT

There are no current plans to commission an independent audit study.

20.2 DISSEMINATION PLANS

The results of the BEACON trial will be of great interest to patients and the public, dermatologists (national/ international), GPs, nurses, pharmacists, scientists interested in eczema and healthcare commissioners. Our dissemination will take into account these different audience types and capitalise on the considerable reach through national clinical networks (British Association of Dermatologists (BAD), UK DCTN (and Centre for Evidence Based Dermatology monthly evidence updates), UK Translational Research Network in Dermatology (UK TREND), British Dermatological Nursing Group (BDNG)), international networks (European Society of Dermatological Research (ESDR), HOME, International Eczema Council), and health economic networks and links.

The primary and secondary outcomes will be published in a peer reviewed open-source medical journal within 12 months of the close of each comparison regardless of the magnitude or direction of effect. We will submit summary articles where possible, including the Dermatological Nursing Journal and the National Eczema Society quarterly magazine "Exchange". The health economic analysis will be presented as a separate publication(s). Additional potentially high impact publications are likely to arise around lessons learned from the trial conduct and setting up the trial as a platform for future trial arms. We will publish the trial protocol.

We will submit the BEACON trial results to key international dermatology conferences including the BAD Annual Meeting (35% of UK dermatologists attend), ESDR, the European Academy of Dermatology and Venereology, the American Academy of Dermatology (AAD), the International Symposium on Atopic Dermatitis and the World congress of Dermatology. Results will be submitted to the BDNG and the Society for Academic Primary Care (SAPC) Dermatology Specialist Interest Group meeting to reach other professional healthcare groups. We will hold a stakeholder workshop with the National Eczema Society (NES) to disseminate the results of the trial as soon as available. Dermatologists and other healthcare professionals from recruiting sites will be invited, as well as other prominent UK dermatologists, patients, dermatology nurses, and commissioners. In addition to publicising results to key stakeholders, this workshop will provide a platform to understand how the patient and clinical community view the results, informing the proceeding wider dissemination strategy. Results will additionally be shared at information days for patients and study days for clinicians, both routinely run by the NES.

In collaboration with the NES, we will produce digestible plain language summaries in a range of formats to publicise the trial results to different target groups. Infographics will be produced to disseminate our trial findings to a clinical and a wider lay audience. We will produce summaries of the results in written, audio (podcast) and video format involving patient and healthcare professional members of the trial team. Brief versions will be targeted to a lay audience and more detailed versions to the healthcare professional audience. We will provide suggested text and images that can be used for social media posts. The NES will review and amend as necessary its existing patient information resources on systemic treatments, to reflect the research findings. In addition to what is planned, we will seek out ideas for different formats that may emerge over the lifetime of this trial. The trial website will describe the results and link to the summaries in different formats. We would also hope that an NIHR signal would be produced to support our dissemination.

We will ensure that the results of this trial are available for updates to key UK and European guidelines. These will include Technology Appraisal Guidance, Primary Care Dermatology Society and BAD Guidelines for the management of atopic eczema, Scottish Intercollegiate Guidelines Network (SIGN) Management of atopic eczema in primary care and European Guidelines for treatment of atopic eczema.

We will invite a small number of trial participants to provide short testimonials and/or blogs about their participation in the trial. With their permission, we will use these in our publicity materials and website to encourage others to participate and increase retention. We will invite participants of underrepresented ethnic groups or gender to contribute to these.

